9.5 Study timetable and end of study

The end of the study is defined as ‘the last visit of the last subject undergoing the study’.

The study may be terminated at individual centres if the study procedures are not being performed according to GCP, or if recruitment is slow. AstraZeneca may also terminate the entire study prematurely if concerns for safety arise within this study or in any other study with dapagliflozin.

Planned duration of the study:

Study period: February 2011 – April 2012

Registration period: February 2011 – August 2011

Discontinuation or suspension of the whole study programme

If AstraZeneca decides to prematurely terminate or suspend the study, the Principal Investigator, the head of the institution, and regulatory authorities should receive written notification of the reasons for the premature termination or suspension.

The Principal Investigator will immediately notify the decision to the subjects, give appropriate medical treatment; take necessary measures, and record treatment or measures provided on the source documents.

Completion of the study

Upon terminating the study, the Principal Investigator will report in writing the completion of the study as well as the summary of the results to the head of the study site in accordance with the institution's rules. The head of the study site, who is informed of the termination by the investigator, will provide a written notification of the results to the IRB and AstraZeneca.

10. DATA MANAGEMENT BY ASTRAZENECA DATA MANAGEMENT CENTRE

Data management will be performed by AstraZeneca Data Management Centre staff.

Data will be entered in the WBDC system at the study site. Trained study personnel will be responsible for entering data on the observations, tests and assessments specified in the protocol into the WBDC system and according to the eCRF Instructions. The eCRF Instructions will also guide the study site in performing data entry.

Data entered in the WBDC system will be immediately saved to a central database and changes tracked to provide an audit trail. The data will then be Source Data Verified (SDV), reviewed, queried and updated as needed. Principal Investigator is responsible for signing the eCRF electronically as per the eCRF instructions.

Data queries will be raised for inconsistent, impossible or missing data. All entries to the study database will be available in an audit trail. Quality assurance procedures will be applied to each stage of data handling to ensure that all data are reliable and have been processed correctly.

The data will be frozen and then locked to prevent further editing. When all data have been coded, validated, signed and locked, clean file will be declared. All editing accesses will be revoked and the final database will be locked. Copy of the eCRF will be archived at the study site when the study has been locked.

The study Data Management Plan will describe in greater detail the methods used to collect, check and process clinical data. It will also clarify the roles and responsibilities of the various functions and personnel involved in the data management process.

Prior to breaking the treatment codes, all decisions on the evaluability of the data from each individual patient must have been made and documented.

Management of external data

Data Management determines the format of the data to be received from external vendors and coordinates the flow of data to an external environment or clinical database (if applicable). Data Management will ensure that the data collection tool (eg, IWRS etc) will be tested / validated as needed. External data reconciliation will be done with the clinical database as applicable.

Dictionary coding

AEs and medical/surgical history will be classified according to the terminology of the latest version the MedDRA. Medications will be classified according to the Bristol-Myers Squibb Drug Dictionary. All coding will be performed by the coding team at Bristol-Myers Squibb.

11. EVALUATION AND CALCULATION OF VARIABLES BY ASTRAZENECA

11.1 Calculation or derivation of efficacy variable(s)

11.1.1 Change and percent change from baseline

Change from baseline will be calculated as absolute difference (or percentage change) between the value measured at or derived for a specific time point after baseline minus baseline value. Baseline is defined as the last value collected on Visit 6 but also before during intake.

Percent change from baseline will be computed as $100 \times (\text{value measured at or derived for a specific time point after baseline} - \text{baseline value}) / \text{baseline value}$.

11.1.2 Last observation carried forward (LOCF)

If no measurement is available at a time point, the last post-baseline measurement prior to the specific time-point will be used instead for analysis. Unless otherwise specified, if a subject initiates rescue medication, the last value taken on or before the first rescue dose will be used for analysis.

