3.1.5 Follow-up period (3weeks)

Subjects will stop taking investigational products at Visit 13 (Week 24) and will be re-evaluated 3 weeks later for AEs and laboratory parameters. Subjects who discontinue study medication during the treatment period will also be re-evaluated 3 weeks later for AEs and laboratory parameters. Open-label use of anti-diabetic agents are permitted during the follow-up period.

Table 2 Study plan

Procedure	Screening Period	Wash-out Period ^a		Lead-in Period		Double-blind, Placebo-controlled Treatment Period								Follow-up Period
	Wk -12 or Wk -6 ^a	Wk -10	Wk -7	Wk -4	Wk -1	Wk 0	Wk 1 ^b	Wk 4 ^b	Wk 8 ^b	Wk 12 ^b	Wk 16 ^b	Wk 20 ^b	Wk 24	Wk 27
Visit	1	2	3	4	5	6	7	8	9	10	11	12	13	14
Visit window (days)	+7	±3	±3	±3	±3	0	±3	±3	±3	±3	±3	±3	±3	±3
Eligibility Assessments														
Informed Consent	X													
Review Inclusion/Exclusion Criteria or Randomization Criteria	X	X	X	X	X	X								
Randomisation						X								
Complete Medical History	X													
Complete Physical Examination	X			X		X							X	
Brief Physical Examination		X	X				X	X	X	X	X	X		X
Vital Signs, Body Weight	X			X		X	X	X	X	X	X	X	X	X
Height	X													
Orthostatic Blood pressure						X	X	X	X				X	X
BMI	X					X							X	X
Waist Circumference	X					X							X	
ECG	X					X							X	
Concomitant medications	X	X	X	X	X	X	X	X	X	X	X	X	X	X
General														
Dietary/exercise instruction/review		X	X	X	X	X	X	X	X	X	X	X	X	X
Dispense Glucose Meter, diary and provide instructions		X	X	X	X	X	X	X	X	X	X	X	X	

Table 2 Study plan

Procedure	Screening Period	Wash-out Period ^a		Lead-in Period		Double-blind, Placebo-controlled Treatment Period								Follow-up Period
	Wk -12 or Wk -6 ^a	Wk -10	Wk -7	Wk -4	Wk -1	Wk 0	Wk 1 ^b	Wk 4 ^b	Wk 8 ^b	Wk 12 ^b	Wk 16 ^b	Wk 20 ^b	Wk 24	Wk 27
Visit	1	2	3	4	5	6	7	8	9	10	11	12	13	14
Visit window (days)	+7	±3	±3	±3	±3	0	±3	±3	±3	±3	±3	±3	±3	±3
Safety Assessments														
AE Assessment				X	X	X	X	X	X	X	X	X	X	X
SAE Assessment	X	X	X	X	X	X	X	X	X	X	X	X	X	X
Hypoglycemic Events Assessment				X	X	X	X	X	X	X	X	X	X	X
Laboratory Tests														
Pregnancy Test (urine) (WOCBP only)	X			X		X	X	X	X	X	X	X	X	X
Standard Safety Laboratory Panel (Blood and urine)	X			X		X	X	X	X	X	X	X	X	X
HbA1c	X				X	X		X	X	X	X	X	X	X
FPG	X	X	X	X	X	X	X	X	X	X	X	X	X	X
Fasting Insulin, C-peptide	X					X			X		X		X	
Glycoalbumin	X					X		X	X	X	X	X	X	
Spot urine collection for glucose, sodium and creatinine	X					X			X		X		X	

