Fasting serum lipids: TC, LDL-C, HDL-C, TG, and FFA						X							X	
Hepatitis Screen Panel ^c , TSH, and PT/PTT	X													
Cystatine C						X							X	
Parathormone (PTH)						X							X	X

Table 2 Study plan

Procedure	Screening Period	Wash-out Period ^a		Lead-in Period		Double-blind, Placebo-controlled Treatment Period								Follow-up Period
	Wk -12 or Wk -6 ^a	Wk -10	Wk -7	Wk -4	Wk -1	Wk 0	Wk 1 ^b	Wk 4 ^b	Wk 8 ^b	Wk 12 ^b	Wk 16 ^b	Wk 20 ^b	Wk 24	Wk 27
Visit	1	2	3	4	5	6	7	8	9	10	11	12	13	14
Visit window (days)	+7	±3	±3	±3	±3	0	±3	±3	±3	±3	±3	±3	±3	±3
Clinical Drug Supplies														
Dispense Study Medication				X		X		X	X	X	X	X	X	
Review Medication Compliance					X	X	X	X	X	X	X	X	X	X

FFA: free fatty acid, TSH: thyroid stimulating hormone, PT: prothrombin time, PTT: partial thromboplastin time, WOCBP: Women of child bearing potential

- a Wash-out period is applicable only for subjects with ongoing treatment with anti-diabetic agents. For treatment-naïve subjects, screening period is Week -6 to -4.
- b Subjects not completing the treatment period should complete the procedures described for Visit 13 within 7 days after discontinuation. These subjects should also complete the procedures described for a follow-up visit (ie, Visit 14) three weeks after discontinuation of investigational product.
- c Includes anti-HAV (IgM, IgG), HBsAg, anti-HBc (igG, IgM) and anti-HCV.

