5.8.2 Procedures for discontinuation of a subject from investigational product

A subject that discontinues will always be asked about the reason(s) for discontinuation and the presence of any AEs. The Principal Investigator/sub-investigator will perform the best possible observation(s), test(s) and evaluation(s) as well as give appropriate medication and all possible measures for the safety of the subject. They will also immediately inform AstraZeneca of the withdrawal. AEs will be followed up (See Sections 6.4.3 and 6.4.4); diary, glucometer and study drug should be returned by the subject.

Randomised subjects

Randomised subjects who discontinue the study treatment before Week 24 should return and complete the procedures described for Visit 13 as soon as possible but at the latest 7 days after discontinuation. These subjects should also be scheduled for a follow-up visit (ie, procedures of Visit 14) three weeks after discontinuation of investigational product. In addition subjects who discontinue the study due to an AE including a laboratory abnormality should be followed by the investigator until the event has been resolved or stabilised.

After discontinuation of investigational product alternative anti-diabetic treatment will be initiated according to the investigator's judgement and according to local medical practice.

Subjects with an increased CK >10X ULN will have their investigational product held and repeated CK test preferably within 24 hours, but not exceeding 72 hours. If repeated CK is still >10X ULN the subject should permanently discontinue all study medication and be withdrawn from the study (in which case an Adverse Event must be reported). Otherwise investigational product may be resumed unless otherwise contraindicated.

Subjects with increased liver function tests as defined in Section 5.8.1 under listing No.13 will be scheduled for a follow-up visit within 3 days following the receipt of the result. Subjects may remain on study medication until the confirmatory results are obtained. If repeat liver function tests still are increased as outlined in Appendix G the subject should permanently discontinue study medication and be withdrawn from the study (see Appendix G for further guidance).

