Other secondary outcome variables and exploratory outcome variables shall provide supportive efficacy and safety information regarding the differences between the treatment groups. For other secondary efficacy variables, supportive statistical test will be made at nominal significance level 0.05 and nominal p-values will be reported.

Unless otherwise specified, for all changes (or percent changes) from baseline to a specific time point post-baseline as well as for glycemic therapeutic response definitions, analyses will be based on measurements available at that time point or the last post baseline measurement prior to the time-point, if no measurement is available at that time point, ie, last observation carried forward (LOCF). For rescued subjects, values collected after initiation of rescue medication will not be considered in calculating the LOCF values for glycemic endpoints.

The time course of all continuous variables will be presented using standard descriptive summary statistics.

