12.2.2.1 Primary efficacy analysis

The change in HbA1c from baseline to Week 24 (LOCF), will be analyzed by an analysis of covariance (ANCOVA) model including treatment group and gender as fixed effect and baseline as covariate. The ANCOVA model will be used to derive a least squares estimate of the treatment difference with 95% confidence interval and corresponding 2-sided p-value.

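### Read literally, the LOCF rule lets the off-drug follow-up visit stand as the Week 24 efficacy value for subjects who stop before about Week 21

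*Protocol*

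**What the plan says.** The primary analysis (12.2.2.1) depends on the carry-forward rule: "The change in HbA1c from baseline to Week 24 (LOCF), will be analyzed by an analysis of covariance (ANCOVA) model". Section 12.2.2.2 analyses FPG and body weight in a similar way.

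The rule in 11.1.2 is chronological: "If no measurement is available at a time point, the last post-baseline measurement prior to the specific time-point will be used instead for analysis". Its one exception concerns rescue: "if a subject initiates rescue medication, the last value taken on or before the first rescue dose will be used for analysis". Section 12.2.2 repeats the rule with the same kind of exception: "For rescued subjects, values collected after initiation of rescue medication will not be considered in calculating the LOCF values for glycemic endpoints". Neither section sets a cut-off at the last dose of study drug or at the start of other anti-diabetic treatment.

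A randomised subject who stops early completes the Visit 13 procedures within 7 days. Section 5.8.2 then adds: "These subjects should also be scheduled for a follow-up visit (ie, procedures of Visit 14) three weeks after discontinuation of investigational product". Footnote b of Table 2 says the same. Table 2 marks HbA1c, FPG and body weight at Visit 14, and Table 6 confirms the two laboratory measures.

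On treatment after stopping, 3.1.5 states: "Open-label use of anti-diabetic agents are permitted during the follow-up period". Section 5.8.2 goes further: "After discontinuation of investigational product alternative anti-diabetic treatment will be initiated according to the investigator's judgement".

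**The concern.** The rescue exception does not reach treatment started after discontinuation. Section 3.1.4.1 defines rescue narrowly: named agents, started under the FPG criterion of Table 1, from Week 12. Study-specific discontinuation criterion 7 in 5.8.1 treats other anti-diabetic agents as a separate category. A Visit 14 value taken on newly started open-label therapy is therefore still eligible to be carried forward.

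Such a value does not measure what the trial sets out to measure. The objective in 2.1 is the change after 24 weeks of double-blind treatment. Section 3.2.1 gives the follow-up period the purpose of examining reversibility.

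The rule can also treat similar events in opposite ways. Rescue opens only at Week 12. Section 6.4.9.1 discontinues subjects whose high self-monitored FPG is confirmed by the central laboratory, and that can happen earlier. A subject rescued at Week 14 is analysed on a pre-rescue value. A subject discontinued at Week 8 for poor control would be analysed on a Week 11 value, off study drug and perhaps on other therapy. If such failures are commoner on placebo, the treatment difference shrinks.

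**Working it through.** **1. The plan's own sample size (12.3).** Inputs: difference 0.5, SD 0.9, two-sided alpha 0.027, power 90%.

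- n = 2 × (2.211 + 1.282)² × 0.9² / 0.5² = 2 × 12.20 × 0.81 / 0.25 = 79.1, rounded up to 80 per group.
- Inflation: 80 / 0.95 = 84.2, rounded up to 85 per group, 255 in total.
- Two-sample noncentral-t power with 80 per group (158 df): noncentrality 0.5 / (0.9 × √(2/80)) = 3.51, power 89.9%.

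The stated figures reproduce and are not in dispute. The 5% in 12.3 is the share with no post-baseline value, not a discontinuation rate.

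**2. When Visit 14 comes before Week 24.** Inputs: Week 24 is Day 24 × 7 = 168. A discontinuer's Visit 14 is due 21 days after stopping, and Table 2 gives it a window of ±3 days.

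- Visit 14 precedes Week 24 if stop day + 21 < 168, that is, a stop before Day 147 (Week 21). With the window, the limit is Day 144 to 150.
- The termination visit is at most 7 days after stopping, so Visit 14 is later and is the last value before Week 24.
- Example: stop on Day 56 (Week 8), termination visit by Day 63, Visit 14 on about Day 77 (Week 11). Nothing later precedes Day 168.

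If stopping times were uniform over 24 weeks (an assumption), 21/24 = 87.5% of discontinuers would be caught, provided they attend Visit 14 and were not already rescued.

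**3. Effect on power.** Let d be the share of each arm whose endpoint is a Visit 14 value, and k the share of the HbA1c effect still present. Both are assumptions. The diluted difference is 0.5 × (1 − d × (1 − k)). With k = 0.5, 80 per group, SD 0.9 and alpha 0.027:

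| d | Diluted difference | Power |
|---|---|---|
| 0% | 0.500 | 89.9% |
| 5% | 0.4875 | 88.3% |
| 10% | 0.475 | 86.4% |
| 15% | 0.4625 | 84.5% |

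If 5% to 15% is instead the overall discontinuation rate with uniform timing, the affected share is 4.4% to 13.1%. The difference is then 0.489 to 0.467. Power by normal approximation is 89.0% to 85.8%, against 90.4% undiluted by the same method.

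**4. Sensitivity to the SD.** Section 12.3 reports an SD of about 0.52 in the Japanese Phase IIb study. Even with d = 15% and nothing retained (difference 0.425), power is 99.8% at SD 0.52 and 94.5% at an assumed SD of 0.7.

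**The case against.** The strongest reply is that visits carry week labels. Tables 2 and 6 equate Visit 13 with Week 24 and Visit 14 with Week 27. If data are slotted by label, the early-termination Visit 13 record becomes the Week 24 value, carry-forward is not triggered, and Visit 14 is never prior to Week 24. Context supports this reading: 12.2.3 adds follow-up data expressly to the safety evaluation, and no efficacy section does so. Visit mapping is also ordinary material for a statistical analysis plan, which section 12 promises, and 5.4.2 requires evaluability decisions before the codes are broken.

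Much of this stands. A reader might infer that off-drug values are bound to enter the primary endpoint. The documents do not support that, because the outcome depends on a mapping the protocol leaves unstated. What remains is that 11.1.2 is a rule already stated, not a gap. Applied by date, it gives the wrong value, so an analysis plan that excluded Visit 14 would be correcting it.

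A reader might also infer a much larger power loss, down to 77.4%. That figure needs 15% affected and no HbA1c effect left at three weeks. Section 3.2.1 says HbA1c takes 8 to 12 weeks to stabilise after oral agents are stopped, so complete loss at three weeks is implausible for the primary endpoint, though FPG could lie closer to it. The 89.9% comparator is itself generous: it credits early stoppers with the full 24-week effect, which their on-treatment values may not show either.

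**Conclusion.** The point holds for the literal wording of 11.1.2 and 12.2.2. It affects subjects who stop before about Week 21, attend Visit 14 and were not already rescued. It touches HbA1c, FPG and body weight, and it contradicts the stated objective and the stated purpose of follow-up. It is not certain to occur in the analysis.

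The size is modest: at SD 0.9, power of 88.3% to 84.5% instead of 89.9%, if 5% to 15% of each arm are affected equally and half the HbA1c effect is retained. Neither input is in the protocol, and a smaller SD makes the loss smaller. The simple model leaves out open-label therapy. Dilution is the likelier direction, but unequal discontinuation or unequal open-label use could move the estimate either way.

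A reader might infer a threat to the Type I error rate; none is shown. This is a defect of wording worth correcting before unblinding, not a flaw in the design or the sample size.

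**What to change.** In 11.1.2 and 12.2.2, state that:

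- carry-forward for Week 24 efficacy uses treatment-period values only, including the early-termination Visit 13 assessment made within the 7 days already allowed;
- Visit 14 follow-up values are never carried forward;
- values taken after the start of any non-study anti-diabetic agent, rescue or not, are never carried forward.

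The same sentence should say whether the short insulin courses permitted in 5.6 trigger that last cut-off, since a literal reading would discard everything after a brief course.

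The cost is a short text change in the protocol, the same rule in the analysis plan, and some programming. No new data are needed, because 5.6 and 5.7 already have medication dates and study drug administration recorded in the eCRF. A tighter window for FPG is not needed and could discard termination-visit values that 5.8.2 allows. A mixed model for repeated measures is not needed for this correction either.

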11.2 Calculation or derivation of safety variable(s)

11.2.1 Calculation of eGFR

The following Japan guideline recommended equation will be used to calculate eGFR.

$$\text{eGFR (mL/min/1.73m}^2\text{)} = 194 \times (\text{SCr})^{-1.094} \times (\text{age})^{-0.287} \times (0.739 \text{ if female})$$

11.2.2 Other significant adverse events (OAE)

During the evaluation of the AE data, an AstraZeneca medically qualified expert will review the list of AEs that were not reported as SAEs and Discontinuation of Investigational Product due to

Adverse Event (DAEs). Based on the expert's judgement, significant AEs of particular clinical importance may, after consultation with the Global Patient Safety Physician, be considered OAEs and reported as such in the Clinical Study Report. A similar review of laboratory/vital signs/ECG data will be performed for identification of OAEs.

Examples of these are marked haematological and other laboratory abnormalities, and certain events that lead to intervention (other than those already classified as serious), dose reduction or significant additional treatment.

- 11.3 Calculation or derivation of patient reported outcome variables – Not applicable**
- 11.4 Calculation or derivation of pharmacokinetic variables – Not applicable**
- 11.5 Calculation or derivation of pharmacodynamic variable(s) – Not applicable**
- 11.6 Calculation or derivation of pharmacogenetic variables – Not applicable**
- 11.7 Calculation or derivation of health economic variables – Not applicable**

12. STATISTICAL METHODS AND SAMPLE SIZE DETERMINATION BY ASTRAZENECA

A comprehensive statistical analysis plan will be finalized prior to the clean file.

12.1 Description of analysis sets

Protocol deviations will be reviewed in a blinded fashion by the study team prior to database lock. All decisions to exclude subjects and/or data from the Full Analysis Set to form the Per Protocol Analysis Set will be made prior to the unblinding of the study and agreed by the study team.

12.1.1 Efficacy analysis set

The evaluation of efficacy will be performed primarily for the full analysis set.

12.1.1.1 Full analysis set

The full analysis set will include all randomised subject who received at least one dose of study medication, and who have a non-missing baseline value and at least one post-baseline efficacy value for at least one efficacy variable. The subjects will be analysed according to the treatment group to which they were randomised, regardless of the actual treatment taken.

12.1.1.2 Per protocol analysis set

The per-protocol analysis set – being a subset of the full analysis set – will include all subjects of the full analysis set without major protocol deviations which may affect the study outcome significantly. The subjects will be analysed according to the treatment group to which they were randomised, regardless of the actual treatment taken. All decisions to exclude subjects from the per-protocol data set will be made prior to the unblinding of the study.

